1.1 Scope of document

The RAP documents contain detailed information to aid the production of Statistics & Programming input into the Clinical Study Report (CSR) for trial “**CQVM149B2203**”.

The Statistical analysis plan (SAP) describes the implementation of the statistical analysis planned in the protocol.

1.2 Study reference documentation

Final study protocol is finalized at the time of the finalization of Statistical Analysis Plan.

This SAP Amendment 1 is based on the final version of the

- Study protocol, v00, 28 Feb 2017

1.3 Study objectives

1.3.1 Primary objectives

- To assess the bronchodilator effect of orally inhaled indacaterol salts (maleate and acetate) in subjects with asthma compared to placebo as measured by trough FEV1 after 14 days of treatment

[figure not shown]
1.3.2 Secondary objective(s)

- To assess the steady state pharmacokinetics of indacaterol after 14 days of treatment of orally inhaled indacaterol salts (maleate and acetate) in subjects with asthma.
- To assess the bronchodilator effect of orally inhaled indacaterol salts (maleate and acetate) in subjects with asthma compared to placebo as measured by:
 - Time to peak FEV1 on Day 14
 - FEV1, FEV1 (% predicted), FVC, FVC (% predicted), FEV1/FVC, and FEF25-75% at each post-dose time point after 14 days of treatment
 - Standardized FEV1 AUC from pre-dose to 4 h post-dose on Day 14 of treatment
- To assess the bronchodilator effect of indacaterol acetate, indacaterol maleate, and placebo by comparing the pre-medication (morning (pre-dose) and evening) peak expiratory flow (PEF) rate collected between days 8 and 14 of each treatment.
- To assess rescue medication usage for indacaterol salts (maleate and acetate) in comparison to placebo.
- To assess the safety and tolerability of indacaterol salts (maleate and acetate) in comparison to placebo of 14 days of treatment in each treatment period.

Corporate Confidential Information

1.4 Study design and treatment

Figure 1-1 Study design

This is a confirmatory, randomized, double blind, placebo-controlled, three-period complete block, crossover study in patients with asthma.

Subjects who meet all of the eligibility criteria will be randomized to one of six treatment sequences as described in [Figure 3-1](#). They will receive their first dose on the morning of Day 1. Subjects will be dosed between 06:00 a.m. and 10:00 a.m. under the guidance and supervision of the investigator or designee after an additional training for correct use of the Concept1 inhalation device. Dosing of investigational product and background ICS medication should occur at approximately the same time of the day throughout the study. PEF measurements (if not already performed at home on the morning of Day 1 or Day 14) should be taken prior to pre-dose spirometry and safety assessments.

On Day 1, subjects will leave the clinic after the completion of the required assessments and will dose at home once daily in the morning on Days 2 to 13. During days 2 -13, subjects will record drug administration, PEF measurements, mouth rinsing, and rescue medication use in their diary. Subjects will be domiciled at the clinic on the morning of Day 14, for drug administration and Day 14 visit assessments. Subjects will be discharged on Day 15 following the final PK and safety blood sample draw and completion of Day 15 assessments.

A washout period of 7 - 14 days will separate each treatment period.

Epoch Completion assessments must be conducted for subjects who complete all three treatment periods or at any time a subject early terminates from the trial. The last visit (Day 65) of Treatment period 3 will also be the end of study visit. Subjects should be discharged from the site after the completion of Day 15 assessments for all 3 periods.

2 First interpretable results (FIR)

First interpretable results (FIR) will be provided for this trial.
Corporate Confidential Information

Corporate Confidential Information

4 Statistical methods: Analysis sets

For all analysis sets, subjects will be analyzed according to the study treatment(s) received.

The safety analysis set will include all subjects that received any study drug.

The PK analysis set will include all subjects with at least one available valid (i.e. not flagged for exclusion) PK concentration measurement, who received any study drug and experienced no major protocol deviations with relevant impact on PK data.

The PD analysis set will include all subjects with any available PD data, who received any study drug and experienced no protocol deviations with relevant impact on PD data.

The PD analysis set will include all subjects with available PD parameter data who received any study drug and experienced no major protocol deviations with relevant impact on PD data. Any PD data for the primary endpoint obtained within 6 hours after rescue medication use or within 7 days of systemic corticosteroid will be set to missing.

The analysis sets and protocol deviation codes are related as follows:

Table 4-1 Protocol deviation codes and analysis sets

Category Deviation code	Text description of deviation	Data exclusion
Subjects are excluded from Safety analysis in case of these PDs:		
INCL01	Deviation from inclusion criteria: In the unlikely event that a subject was included without written informed consent, then their data will not be used	Exclude subject from Safety analysis set Yes
Subjects are excluded from PD analysis in case of these PDs:		
INCL01	Deviation from inclusion criteria: In the unlikely event that a subject was included without written informed consent, then their data will not be used	Exclude subject from PD analysis set Yes
Subjects are excluded from PK analysis in case of these PDs:		
INCL01	Deviation from inclusion criteria: In the unlikely event that a subject was included without written informed consent, then their data will not be used	Exclude subject from PK analysis sets Yes

If updates to this table are needed, an amendment to the SAP needs to be implemented prior to DBL.

5 Statistical methods for Pharmacokinetic (PK) parameters

5.1 Variables

The concentrations of indacaterol in plasma will be determined by a validated LC-MS/MS method;

Corporate Confidential Information

Corporate Confidential Information

Other pharmacokinetic parameters may be determined as appropriate.

5.2 Descriptive analyses

Indacaterol plasma concentrations will be listed by treatment sequence, subject, profile day, and sampling time point. Descriptive summary statistics will be provided by treatment, profile day, and sampling time point. Summary statistics will include mean (arithmetic and geometric), SD, CV (arithmetic and geometric), median, minimum and maximum.

Concentrations below LLOQ will be treated as zero in summary statistics. A geometric mean will not be reported if the dataset includes zero values.

Pharmacokinetic parameters will be listed by treatment sequence, profile day, and subject. Descriptive summary statistics will be provided by treatment and profile day. Summary statistics will include mean (arithmetic and geometric), SD, and CV (arithmetic and geometric), median, minimum and maximum. An exception to this is Tmax where median, minimum and maximum will be presented.

5.3 Statistical model, assumptions and hypotheses

The log transformed pharmacokinetic parameters AUC0-24h,ss and Cmax,ss on day 14 will be compared for indacaterol acetate (test) relative to indacaterol maleate (reference) using a mixed effects model with sequence, treatment and period as fixed effects and subject nested within sequence as random effect. Body weight assessed in period 1 will be included as a continuous covariate and applied as a fixed effect in the model. The estimates of the treatment differences (indacaterol acetate (test) vs. maleate (reference); Frel) along with their 90% confidence intervals will be obtained. The estimates and confidence intervals will be transformed back to the original scale to provide ratios of the geometric means together with their corresponding 90% confidence intervals.

Tmax,ss will be analyzed using non-parametric methods. The median difference and the 90% confidence interval of the median difference in Tmax,ss will be estimated using Hodges-Lehmann estimation procedure.

5.3.1 Model checking procedures

All drug concentrations below the lower limit of quantification (LLOQ) will be reported as "zero" and will be treated as zero for calculation of PK parameters.

Subjects with missing PK parameters (e.g. Cmax,ss, and AUC0-24h,ss) in some but not all periods will be included in a mixed model analysis.

5.3.2 Graphical presentation of results

Individual concentration-time profiles and mean profiles with SD bars will be presented for Day 14 PK data.

6 Statistical methods for Pharmacodynamic (PD) parameters

6.1 Primary objective

The primary objective is to assess the bronchodilator effect of orally inhaled indacaterol salts (maleate and acetate) in subjects with asthma compared with placebo as measured by trough FEV1 after 14 days of treatment.

6.1.1 Variables

The primary variable is trough FEV1 after 14 days of treatment. Trough FEV1 is defined as the average of the FEV1 measurements at 23 h 15 min and 23 h 45 min post dose.

6.1.2 Descriptive analyses

Trough FEV1 will be listed by treatment sequence, subject and visit/time and descriptive summary statistics will be provided by treatment and visit/time. Summary statistics will include arithmetic mean, SD, CV (arithmetic), median, minimum and maximum.

6.1.3 Statistical model, assumptions and hypotheses

The following hypothesis will be tested for each of indacaterol salts (acetate and maleate) versus placebo separately:

H0 (Null Hypothesis): There is no difference in terms of the trough FEV1 after 14 days of treatment between:

Indacaterol acetate and placebo
OR
Indacaterol maleate and placebo

H1 (Alternative Hypothesis): There is a difference in terms of the trough FEV1 after 14 days of treatment between:

Indacaterol acetate and placebo
AND
Indacaterol maleate and placebo

No adjustments will be made for multiplicity because the objective is to prove that both formulations must be statistically significantly different from placebo each at 2-sided 5% level of significance.

The trough FEV1 after 14 days of treatment will be analyzed using an analysis of variance (ANOVA) with treatment, period and sequence as fixed effects and subject nested within sequence will be included as a random effect. The Kenward-Roger approximation will be used to estimate denominator degrees of freedom.

The final model estimates will include the LS mean for each treatment (indacaterol acetate, maleate and placebo) together with standard error (SE), the adjusted mean difference between indacaterol salts (acetate and maleate) and placebo, and corresponding two-sided 95% confidence intervals and P-value for the differences (acetate vs placebo and maleate vs placebo) using placebo as reference treatment.

Additionally as a secondary consideration, an estimate of the differences in trough FEV1 between indacaterol acetate (test) and indacaterol maleate (reference) will be calculated together with the corresponding two sided 95% confidence intervals.

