³ A washout (minimum of 7 days and maximum of 14 days from last dose on Day 14) must occur after completion of Treatment period 1 prior to beginning Treatment period 2 and after completion of Treatment period 2 prior to beginning Treatment period 3. There is no washout after Day 15 of Treatment period 3. A + 2 days washout window is allowed for each treatment. Study days are based on a 10 days washout period, Visit days may be adapted as per the actual washout period; 7-14 days allowed per protocol.

⁴ Assessments to be performed if subject terminates early or at V399 Study completion.

⁵ Pre-dose assessments on Day 1 may be completed any time on Day 1 prior to first dose. For Treatment period 1 only: Pre-dose, Day 1 assessments (with the exception of blood pressure, pulse, spirometry, PEF, diary entry, and device training) do not need to be repeated if screening assessments were completed within 7 days of Day 1 in Treatment period 1. All Day 1, pre-dose assessments must be completed for Treatment period 2 and 3.

⁶ Pre-dose assessments with the exception of spirometry may be completed any time on Day 14 prior to dosing

⁷

Corporate Confidential Information

⁹ Pregnancy assessments may be performed at a greater frequency if required by local regulations.

¹⁰ Serum pregnancy test

¹¹ Urine pregnancy test.

¹² For Treatment periods 2 and 3, dosing on site on Day 1 should be between 06:00am and 10:00am and +/-1h of the time on dosing on Day 1 of Treatment period 1.

¹³ For Treatment periods 1, 2 and 3 dosing on site on Day 14 should be between 06:00am and 10:00am and +/-1h of the time of dosing on Day 1 of the current Treatment Period.

¹⁴ At home study drug administration should be between 06:00am and 10:00am and +/-1h of the time on dosing on Day 1 of Treatment period 1.

¹⁵ Can be repeated once during screening if necessary

¹⁶ Both standing and supine/sitting blood pressure measurements are required at screening and at pre-dose Treatment period 1 only. Only sitting or supine blood pressure measurements are required for other visits. Subjects' positions during blood pressure collections should remain consistent between visits (sitting or supine throughout the study).

¹⁷ This assessment is completed on Day 65 of Treatment period 3 only

¹⁸ If value is outside the acceptable reference range, this assessment may be retested

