11.4.2 Statistical model, hypothesis, and method of analysis

The following hypothesis will be tested for each of indacaterol salts (acetate and maleate) versus placebo separately:

- HA₁: Indacaterol acetate is different to placebo in terms of the trough FEV₁ after 14 days of treatment
- HA₂: Indacaterol maleate is different to placebo in terms of the trough FEV₁ after 14 days of treatment

The trough FEV₁ after 14 days of treatment will be analyzed using an analysis of variance (ANOVA) with treatment, period and sequence as fixed effects and subject nested within sequence will be included as a random effect. The Kenward-Roger approximation will be used to estimate denominator degrees of freedom.

The final model estimates will include the LS mean for each treatment (indacaterol acetate, maleate and placebo) together with standard error (SE), the adjusted mean difference between indacaterol salts (acetate and maleate) and placebo, and corresponding two-sided 95% confidence intervals and P-value for the differences (acetate vs placebo and maleate vs placebo) using placebo as reference treatment. Additionally as a secondary consideration, an estimate of the differences in trough FEV₁ between indacaterol acetate (test) and indacaterol maleate (reference) will be calculated together with the corresponding two sided 95% confidence intervals.

Trough FEV₁ will be listed by treatment sequence, subject and visit/time and descriptive summary statistics will be provided by treatment and visit/time. Summary statistics will include arithmetic mean, SD, CV (arithmetic), median, minimum and maximum.

Graphical methods will be employed to show mean and individual figures for trough FEV₁

No adjustments will be made for multiplicity because the objective is to prove that both formulations must be statistically significantly different from placebo each at 2 sided 5% level of significance.

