11.7 Sample size calculation

Sample size calculations are based on the primary endpoint of trough FEV₁. Trough FEV₁ is defined as the average of the FEV₁ measurements at 23 h 15 min and 23 h 45 min post-dose.

The primary objective is to prove that the test formulation (the one included in the combination therapy which is acetate and maleate salt) must be better than placebo. Using an estimate of within subject standard deviation of 230 mL from Study QAB149D2301 and assuming the data are normally distributed, 42 (7 per sequence) subjects are required to detect the difference of 170 mL in trough FEV₁ with 90% power in each test (acetate vs placebo and maleate vs placebo).

No adjustment will be made for multiplicity because the objective is to obtain a statistical separation from placebo for both the comparisons.

The power where both tests are required to meet the overall objective is >81% power, with a two-sided test at a significance level of 5%.

Allowing for a 20% drop out rate, a total sample size of 54 (9 per sequence) subjects will be randomized to six treatment sequences.

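### The primary ANOVA uses no period baseline, and the protocol contradicts itself on whether Day 1 pre-dose FEV1 is measured in periods 2 and 3; if it is, a pre-specified covariate would buy a modest gain in precision

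*SAP*

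**What the plan says.** **Model.** SAP 6.1.3 has trough FEV1 "analyzed using an analysis of variance (ANOVA) with treatment, period and sequence as fixed effects". Its only other term is a random effect for each patient within sequence. Protocol 11.4.2 specifies the same model: "with treatment, period and sequence as fixed effects and subject nested within sequence will be included as a random effect". Peak FEV1 and standardized FEV1 AUC0-4h borrow it (Protocol 11.5.1, SAP 6.2.3). Neither document gives any of these models a baseline term, or a reason for leaving one out.

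**Collection.** In Protocol 8.1, the table of highly repetitive assessments marks spirometry at -1 h for visits 101, 201 and 301 (nominal Days 1, 26 and 51). The footnotes add: "All Day 1, pre-dose assessments must be completed for Treatment period 2 and 3". For period 1 they exempt spirometry from the waiver that lets recent screening results stand in for Day 1 assessments.

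Protocol 3.1 says otherwise: Day 1 pre-dose spirometry is done before Treatment period 1 only. The same sentence then sends the reader to the assessment schedule for periods 2 and 3. The glossary defines a single baseline, before period 1. Protocol 8.5.1 and SAP 6.2.1 list clock times only for Days 14 and 15. The pre-dose values there follow 13 days of dosing, so they cannot serve as baselines. SAP 1.4 restates the design without the Section 3.1 restriction.

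**The concern.** A random subject effect removes a patient's stable level of FEV1. It does not remove that patient's drift from one period to the next, for example after an infection or a change in ICS adherence. That drift is part of the 230 mL within-subject SD, and FEV1 measured at the start of the period could capture some of it.

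Both salts must separate from placebo, so the residual within-subject variance drives the chance of overall success. It also sets the width of the acetate-minus-maleate interval. If the period baselines are being measured, the plan leaves some precision unused. If they are not, the schedule and Section 3.1 give sites contradictory instructions.

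**Working it through.** **1. The plan's own figures (Protocol 11.7).** Inputs: "Using an estimate of within subject standard deviation of 230 mL from Study QAB149D2301"; "42 (7 per sequence) subjects are required to detect the difference of 170 mL in trough FEV₁ with 90% power in each test"; two-sided 5%.

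- SE of a treatment difference = 230 × √(2/42) = 50.2 mL.
- Residual df = 126 observations − 42 subjects − 2 for period − 2 for treatment = 80.
- Power per test by noncentral t at 170/50.2 = 3.39 is 91.7%. Ninety per cent needs 40 subjects, and the next multiple of six sequences is 42.
- Joint power: the protocol says "The power where both tests are required to meet the overall objective is >81% power", which matches 0.9 × 0.9 = 0.81. Allowing for the shared placebo arm (correlation 0.5 between the two contrasts) it is 86%.
- Dropout: 42/0.8 = 52.5, hence 53, rounded to 54.

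The design reproduces.

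**2. If only the period 1 value exists.** It is constant within a subject, so the subject effect absorbs it. In a simulation of the 42-subject six-sequence design with complete data, the SE was the same with and without it at every correlation tried (49.95 mL both ways at zero correlation). The gain is zero.

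**3. If every period has a value.** Let ρ be the subject-centred correlation of a period's Day 1 FEV1 with its trough. Then adjusted SE = 50.2 × √(1 − ρ²), on 79 df. The documents give no ρ.

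| ρ (assumed) | SE, mL | Fall in SE | Power per test, 170 mL | Joint power, 170 mL | 95% CI half-width, mL |
|---|---|---|---|---|---|
| no covariate | 50.2 | – | 91.7% | 86.0% | 99.9 |
| 0.14 | 49.7 | 1% | 92.2% | 86.8% | 98.9 |
| 0.2 | 49.2 | 2% | 92.7% | 87.5% | 97.9 |
| 0.3 | 47.9 | 5% | 93.9% | 89.5% | 95.3 |
| 0.4 | 46.0 | 8% | 95.5% | 92.0% | 91.6 |
| 0.46 | 44.6 | 11% | 96.5% | 93.7% | 88.7 |

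**4. What ρ is plausible.** Take baselines on Days 1, 26 and 51 and troughs on Days 15, 40 and 65. Assume serial correlation that decays exponentially with a time constant of 14, 28 or 60 days.

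- No measurement noise: ρ = 0.21, 0.35, 0.46.
- 30% of the variance as independent noise: ρ = 0.14, 0.21, 0.23.

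The values are modest because a trough lies 14 days from its own baseline (15 − 1) but only 11 from the next one (26 − 15).

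**5. Cost if ρ = 0.** The simulated SE rises from 49.95 to 50.26 mL, or 0.6%.

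**6. Leakage from residual drug.** Suppose, purely for illustration, that 20 mL of bronchodilation remained at the baseline following an active period. In the six sequences, a placebo period 2 or 3 always follows an active treatment, while a given salt does so half the time. Averaged over three periods, the baseline shift is (2/3) × 20 = 13.3 mL for placebo and (2/3) × 10 = 6.7 mL for a salt, a difference of 6.7 mL. With equal within-subject SDs at baseline and trough, the slope equals ρ. The salt-versus-placebo estimate then moves up by 0.14 × 6.7 = 0.9 mL to 0.46 × 6.7 = 3.1 mL.

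**7. Change from baseline is not a substitute.** Its SD is 230 × √(2(1 − ρ)). At ρ = 0.4 that is 252 mL and power falls to 86%; it beats the unadjusted model only when ρ exceeds 0.5.

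**The case against.** The strongest reply is that the data may not exist. Section 3.1 and the glossary point to one baseline before period 1, and on that reading there is nothing to add. This stands, and it makes the fix conditional.

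Second, the planned ANOVA is valid and meets its stated power, so adjustment is a refinement. This also stands.

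Third, the period 2 and 3 baselines are measured after earlier treatment. Protocol 3.2 derives about 12 days from five effective half-lives but allows a 7-day washout. At half-lives of 40 to 56 h, 0.5^(168/40) = 5% to 0.5^(168/56) = 12.5% of drug would remain after 7 days. Against that, the protocol puts the FEV1 effect at about 48 hours after the last dose, and even a 20 mL residual would move the estimate by only about 1 to 3 mL.

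A reader might infer a much larger loss: at ρ = 0.6 the SE would fall by 20%, to 40.2 mL, and joint power would reach 98%. Nothing in the documents supports that correlation, and it lies above every value that the visit spacing gave in step 4.

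A reader might also infer that bridging between the salts is weakened. Protocol 3.4 says the study is not adequately powered for a direct comparison of the salts. SAP 6.1.3 makes the FEV1 difference a secondary consideration, and no FEV1 interval criterion is set.

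**Conclusion.** The point holds as a conditional efficiency gain joined to a contradiction in the protocol. The primary model has no period baseline. The assessment schedule says that one is measured in every period, and Section 3.1 says that it is not. If it is measured, the covariate should lower the SE by about 1% to 11% and raise joint power at 170 mL from 86% to between 87% and 94%. If it is not, the gain is zero.

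These sizes rest on 42 completers, a within-subject SD of 230 mL, and an assumed ρ of 0.14 to 0.46. They also assume that the 230 mL did not itself come from a baseline-adjusted model, which the documents do not say.

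The omission should not be read as a source of bias or as leaving the trial short of its stated power. The documents support neither. Nor does the 106 mL effect reported for acetate 150 µg at Week 12 of the earlier parallel-group study (Protocol 1.3.3) change this. At that effect, joint power is 39% without the covariate and 40% to 50% with it over the same range. That is a question about the assumed effect size, and a covariate does not settle it.

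**What to change.** 1. Reconcile Protocol 3.1 with the assessment schedule and footnotes in 8.1, and align 8.5.1 and SAP 6.2.1 with the result.

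2. If the period 2 and 3 values are collected, pre-specify two covariates in SAP 6.1.3 and Protocol 11.4.2, and in the AUC0-4h and peak FEV1 models: the subject's mean Day 1 pre-dose FEV1, and the period's deviation from that mean. The split keeps the between-subject slope out of the treatment contrast. Keep the unadjusted ANOVA as a sensitivity analysis.

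3. State how Day 1 values are handled when missing or taken within 6 hours of rescue medication; the present exclusion rules do not cover them as covariates. One option is to set a missing deviation to zero so that the trough is kept. Whatever rule is chosen should be written before unblinding.

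4. If only the period 1 value exists, leave the model as it is.

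Cost: a written protocol amendment to match the SAP change, one or two degrees of freedom, an SE loss under 1% if the baseline proves uninformative, and the slight leakage in step 6. No new measurements are needed if the schedule in 8.1 is the one being followed.
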